3.1 Eligibility Criteria

_____ 3.1.1 Patient must be \geq 18 years of age.

_____ 3.1.2 Patient must have locally advanced unresectable stage IIIC to stage IV melanoma.

_____ 3.1.3 Patient must have BRAF^{V600E} or BRAF^{V600K} tumor genotype based on a CLIA approved assay.

_____ 3.1.4 Patient must have serum LDH $>$ Upper limit of normal per institution standards.

_____ 3.1.5 Patient must have measurable disease by RECIST 1.1. Baseline measurements of sites of disease must be obtained within 3 weeks prior to study randomization.

_____ 3.1.6 Patient must have been treated with prior immune checkpoint inhibitor therapy (anti PD-1 antibody, anti-CTLA-4 antibody or a combination regimen including either or both agents) either in the adjuvant or metastatic setting. Patient may have received investigational agents in combination with standard therapy, as long as it was adhering to the timeframes outlined below in 3.1.6.3.

_____ 3.1.6.1 Patient must have discontinued active immunotherapy (IL-2, interferon, anti-CTLA-4 antibody, anti-PD-1 antibody

Rev Add2

etc.) or chemotherapy at least 4 weeks prior to randomization.

_____ 3.1.6.2 Patient must have discontinued any oral targeted therapy at least 2 weeks prior to randomization.

_____ 3.1.6.3 Patients must not receive any other investigational anticancer therapy during the period on study or the 4 weeks prior to randomization.

_____ 3.1.7 Patient may have been treated with prior adjuvant therapy including combined BRAF and MEK inhibitor therapy. Patients will be eligible if they tolerated this therapy and did not discontinue the therapy due to toxicity AND \geq 6 months have elapsed since the end of adjuvant BRAF and MEK inhibition. If patients received BRAF and MEK inhibitor therapy in the metastatic setting, they are not eligible.

_____ 3.1.8 Patient may have been treated with prior chemotherapy or radiation therapy.

_____ 3.1.9 Patients who are known to be experiencing an objective partial response to immunotherapy at the time of study enrollment are not eligible.

_____ 3.1.10 Patient must have an ECOG performance status of 0 or 1.

_____ 3.1.11 Patients with a prior or concurrent malignancy whose natural history or treatment does not have the potential to interfere with the safety or efficacy assessment of the investigational regimen are eligible for this trial.

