- _____ 3.1.18.3 Current clinically significant uncontrolled arrhythmias. Exception: Patients with controlled atrial fibrillation for >30 days prior to randomization are eligible.
- _____ 3.1.18.4 Acute coronary syndromes (including myocardial infarction and unstable angina), coronary angioplasty, or stenting within 6 months prior to randomization.
- _____ 3.1.18.5 Abnormal cardiac valve morphology (\geq grade 2) documented by echocardiogram unless a cardiologist concludes the valve abnormality is not clinically significant. Patients with grade 1 abnormalities (i.e., mild regurgitation/stenosis) are eligible.
- _____ 3.1.18.6 Patients with known history or current symptoms of cardiac disease, or history of treatment with cardiotoxic agents, should have a clinical risk assessment of cardiac function using the New York Heart Association Functional Classification. To be eligible for this trial, patients should be class 2B or better.

_____ 3.1.19 Patient must be able to swallow and retain oral medication and must not have any clinically significant gastrointestinal abnormalities that may alter absorption such as malabsorption syndrome or major resection of the stomach or bowels.

_____ 3.1.20 Patient with known serious concurrent infection or medical illness, including psychiatric disorders, which would jeopardize the ability of the patient to receive the treatment outlined in this protocol with reasonable safety are not eligible.

- _____ 3.1.21 Patient must not be receiving concurrent therapy for their tumor (i.e. chemotherapeutics or investigational agents). Radiotherapy delivered to palliate pain is allowed as long as it is not targeting a lesion that meets RECIST criteria for progression. Radiation therapy to the surgical bed with gamma knife radiotherapy while on treatment during the first cycle is allowed for small volume surgically resected brain metastases. Gamma knife radiotherapy for known active, asymptomatic small volume CNS lesions may be performed during the first cycle while on study. Radiotherapy for new CNS lesions identified beyond the first cycle is not allowed on study.
- _____ 3.1.22 Patient must not have a known immediate or delayed hypersensitivity reaction or idiosyncrasy to drugs chemically related to study drug, or excipients or to dimethyl sulfoxide (DMSO).

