- _____ 3.1.23 Patient must not have received cytochrome P450 enzyme –inducing anticonvulsant drugs (EIADs) (i.e. phenytoin, carbamazepine, Phenobarbital, primidone or oxcarbazepine) within 4 weeks prior to randomization.
- _____ 3.1.24 Patient must not have a current use of a prohibited medication as described in Section [5.5](#) on Potential for Drug-Drug Interaction.
- _____ 3.1.25 Patient must have the ability to understand and the willingness to sign a written informed consent document. Patients with impaired decision-making capacity (IDMC) who have a legally authorized representative (LAR) or caregiver and/or family member available will also be considered eligible.
- _____ 3.1.26 Patient must have adequate organ and marrow function as defined below (these labs must be obtained \leq 14 days prior to protocol randomization):
 - _____ Absolute neutrophil count \geq 1,500/mcL
ANC: _____ Date of Test: _____
 - _____ Platelets \geq 100,000/mcL
Platelet: _____ Date of Test: _____
 - _____ Total Bilirubin \leq institutional upper limit of normal (ULN)
Total Bilirubin: _____ Institutional ULN: _____
Date of Test: _____
 - _____ AST(SGOT)/ALT(SGPT) \leq 3.0 \times Institutional ULN
ALT: _____ Institutional ULN: _____
Date of Test: _____
AST: _____ Institutional ULN: _____
 - _____ Creatinine \leq 1.5 \times institutional ULN
Creatinine _____ Institutional ULN: _____
Date of Test: _____

- _____ 3.1.27 Human immunodeficiency virus (HIV)-infected patients on effective anti-retroviral therapy with undetectable viral load within 6 months are eligible for this trial.
- _____ 3.1.28 For patients with evidence of chronic hepatitis B virus (HBV) infection, the HBV viral load must be undetectable on suppressive therapy, if indicated.
- _____ 3.1.29 Patients with a history of hepatitis C virus (HCV) infection must have been treated and cured. For patients with HCV infection who are currently on treatment, they are eligible if they have an undetectable HCV viral load.
- _____ 3.1.30 Patient with asymptomatic new or progressive brain metastases (active brain metastases) are eligible if the treating physician determines that CNS specific treatment is not required.

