5.1.6 Concomitant Medication and Procedures
Because HCQ has known effects on P450 enzymes, patients requiring anti-convulsants may be treated with any of the non-enzyme inducing anti-convulsants which include: felbamate, valproic acid, gabapentin, lamotrigine, tiagabine, topiramate, or levetiracetam. The exception is zonisamide which should be avoided, as zonisamide accumulates in red blood cells as does HCQ. For nausea, aprepitant should be avoided. Radiation therapy to the surgical bed with gamma knife radiotherapy while on treatment during the first cycle is allowed for small volume surgically resected brain metastases. Gamma knife radiotherapy for known active, asymptomatic small volume CNS lesions may be performed during the first cycle while on study. If radiotherapy is being delivered while the patient is on study, patients should hold all three study medications for 2 days prior to radiation and resume study medication one day after completion of radiation. Radiotherapy for new CNS lesions identified beyond the first cycle is not allowed on study. All other concomitant medications are permitted.

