5.4.3.7 Management and Dose Modification Guidelines for QTc prolongation

Both dabrafenib and trametinib have been shown to prolong the QTc interval. However, to date, there are no clinical adverse event reports attributable to QTc interval prolongation or manifest cardiac arrhythmias. However, the following recommendations have been developed to minimize the risk of ventricular tachyarrhythmias in patients with metastatic melanoma treated with this regimen:

- Avoid combination with other drugs with potential to lead to prolongation of QTc interval, if possible.
- ECG should be monitored at baseline, and each cycle (monthly) thereafter.

- Monitor ECG weekly until the QTc interval decreases to < 500 msec, or a cardiologist provides documentation that it is safe to resume therapy before reinstituting therapy at a reduced dose.

Table 11: Management and Dose Modification Guidelines for QTcB-Prolongation

(QT interval on electrocardiogram corrected using the Bazett's formula) QTc-Prolongation ^a	Action and Dose Modification
QTcB ≥501 msec (milliseconds)	
Interrupt all three study agents until QTcB prolongation resolves to grade 1 or baseline
 
Test serum potassium, calcium, phosphorus and magnesium. If abnormal correct per routine clinical practice to within normal limits.
 
Review concomitant medication usage for agents that prolong QTc.
 
If event resolves, restart study treatment at current dose level^b
 
If event does not resolve, discuss with a cardiologist, if deemed clinically significant then discontinue study treatment
 
If event recurs, discuss with a cardiologist, if deemed clinically significant then permanently discontinue study treatments

a Based on average QTc value of triplicate ECGs. For example, if an ECG demonstrates a prolonged QT interval, obtain two or more ECGs over a brief period, and then use the averaged QTc values of the three ECGs to determine if study treatments should be interrupted or discontinued.

b If the QTc prolongation resolves to grade 1 or baseline, the patient may resume study treatment.

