5.4.3.12 New primary melanoma

New primary melanomas have been reported in patients treated with dabrafenib. These were identified within the first 5 months of therapy and did not require treatment modification other than excision. Monitoring for skin lesions should occur as described for cuSCC.

5.5 Drug interactions:

Table 16: Prohibited medications with CYP3A or CYP2C* Interactions

PROHIBITED – Strong inducers of CYP3A or CYP2C8, since concentrations of dabrafenib may be decreased	
Class	Drugs
Antibiotics	Rifamycin class agents (e.g., rifampin, rifabutin, rifapentine),
Anticonvulsant	Carbamazepine, oxcarbazepine, phenobarbital, phenytoin, s-mephentyoin
Miscellaneous	bosentan, St-John's wort

PROHIBITED – Strong inhibitors of CYP3A, or CYP2C8 since concentrations of dabrafenib may be increased	
Class/Therapeutic Area	Drugs/Agents
Antibiotics	Clarithromycin, telithromycin, troleandomycin
Antidepressant	Nefazodone
Antifungals	Itraconazole, ketoconazole, posaconazole, voriconazole
Hyperlipidemia	Gemfibrozil
Antiretroviral	ritonavir, saquinavir, atazanavir
Miscellaneous	Conivaptan

Table 17: USE WITH CAUTION: Moderate inhibitors of CYP3A, or CYP2C8 since concentrations of dabrafenib may be increased

Class/Therapeutic Area	Moderate CYP3A and CYP2C8 Inhibitors
Antiarrhythmics	Diltiazem, verapamil
Antibiotic	Erythromycin

Class/Therapeutic Area	Moderate CYP3A and CYP2C8 Inhibitors
Antifungal	Fluconazole
Miscellaneous	Aprepitant
USE WITH CAUTION: Co-administration of these drugs with study treatment may result in loss of efficacy. Monitor patient for loss of efficacy or substitute with another medication.	
Class/Therapeutic Area	CYP3A4, CYP2B6, CYP2C8, CYP2C9, CYP2C19 or Transporter Substrates that May be Affected by Induction
Analgesics	Alfentanil, buprenorphine, celecoxib, codeine, fentanyl, methadone, oxycodone
Antiarrhythmics	Disopyramide, dronedarone, mexiletine, propafenone, quinidine
Antibiotics	Chloramphenicol, doxycycline, erythromycin, moxifloxacin
Anticoagulants/ Antiplatelets	Cilostazole, warfarin
Anticonvulsants	Divalproex, lamotrigine, valproate, zonisamide
Antidepressants and Antipsychotics	Aripiprazole, bupropion, buspirone, desipramine, haloperidol, mirtazapine, pimozide, quetiapine, trazodone, amitriptyline, clomipramine, imipramine
Antidiabetics	Glyburide, saxagliptin, tolbutamide, nateglinide, pioglitazone, repaglinide, rosiglitazone
Antifungals	Caspofungin, fluconazole, terbinafine
Antihistamines	Astemizole, chlorpheniramine, ebastine

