Antihypertensives	Amlodipine, diltiazem, felodipine, nifedipine, nilvadipine, nisoldipine, verapamil
Antimigraine Agents	Diergotamine, eletriptan, ergotamine
Corticosteroids	Dexamethasone, methylprednisolone, oral budesonide
Erectile Dysfunction Agents	Sildenafil, tadalafil, vardenafil
HMG-CoA Reductase Inhibitors	Atorvastatin, lovastatin, simvastatin, rosuvastatin, pravastatin
Hypnotics and Sedatives	Alprazolam, brotizolam, diazepam, estazolam, midazolam, triazolam, zolpidem, zopiclone
Immunosuppressants	Everolimus, sirolimus, tacrolimus
Miscellaneous	Aprepitant, cisapride, darifenacin, digoxin, disopyramide, leflunomide, methohexitol, oral contraceptives, quinine, ranitidine, solifenacin, sulfasalazine, tramadol, tolvaptan, chloroquine, zopiclone
Selective Aldosterone Blockers	Eplerenone
USE WITH CAUTION: Co-administration of drugs that increase gastric pH should be used with caution when administered with dabrafenib as exposure to dabrafenib may be decreased	
pH altering agents	dexlansoprazole, esomeprazole, famotidine, ilaprazole, lansoprazole, omeprazole, pantoprazole, rabeprazole, ranitidine

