8.3.8 Potential Drug Interactions

Drug Interactions Digoxin: Concomitant HCQ/placebo and digoxin therapy may result in increased serum digoxin levels: serum digoxin

levels should be closely monitored in patients receiving combined therapy.

Insulin or antidiabetic drugs: As HCQ/placebo may enhance the effects of a hypoglycemic treatment, a decrease in doses of insulin or antidiabetic drugs may be required.

Drugs that prolong QT interval and other arrhythmogenic drugs: HCQ/placebo prolongs the QT interval and should not be administered with other drugs that have the potential to induce cardiac arrhythmias. Also, there may be an increased risk of inducing ventricular arrhythmias if HCQ/placebo is used concomitantly with other arrhythmogenic drugs.

Mefloquine and other drugs known to lower the convulsive threshold: HCQ/placebo can lower the convulsive threshold. Co-administration of HCQ/placebo with other antimalarials known to lower the convulsion threshold (e.g., mefloquine) may increase the risk of convulsions.

Antiepileptics: The activity of antiepileptic drugs might be impaired if co-administered with HCQ/placebo.

Methotrexate: Combined use of methotrexate with HCQ/placebo has not been studied and may increase the incidence of adverse effects.

Cyclosporin: An increased plasma cyclosporin level was reported when cyclosporin and HCQ/placebo were co-administered.

The following interactions have been observed on treatment with the structurally related substance chloroquine phosphate, and therefore cannot be ruled out for hydroxychloroquine.

Praziquantel: Chloroquine has been reported to reduce the bioavailability of praziquantel.

Antacids and kaolin: Antacids and kaolin can reduce absorption of chloroquine; an interval of at least 4 hours between intake of these agents and chloroquine should be observed.

Cimetidine: Cimetidine can inhibit the metabolism of chloroquine, increasing its plasma level. Concomitant use of cimetidine should be avoided.

Ampicillin: In a study of healthy volunteers, chloroquine significantly reduced the bioavailability of ampicillin.

8.3.9 Patient Care Implications:

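### The co-medication rules do not bar non-study hydroxychloroquine or chloroquine taken for another illness, so a placebo patient may take the drug class under test

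*Combined protocol and SAP*

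**What the plan says.** Five places in the protocol decide what a patient may take alongside study treatment.

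- **Section 5.5, Table 16 (prohibited).** It lists strong inducers and inhibitors of CYP3A or CYP2C8. Neither HCQ nor chloroquine appears.
- **Section 5.5, Table 17 (use with caution).** Chloroquine is in the Miscellaneous row, "tramadol, tolvaptan, chloroquine, zopiclone", as a substrate whose levels induction may lower. The instruction for that list is "Monitor patient for loss of efficacy or substitute with another medication". HCQ is not listed.
- **Section 5.1.6.** After naming a few drugs to avoid and limiting radiotherapy, it says "All other concomitant medications are permitted".
- **Criterion 3.1.24.** "Patient must not have a current use of a prohibited medication as described in Section" 5.5. It therefore screens against the Section 5.5 prohibited drugs only.
- **Criteria 3.1.6.3 and 3.1.21.** These bar anticancer use: "Patients must not receive any other investigational anticancer therapy during the period on study or the 4 weeks prior to randomization" and "Patient must not be receiving concurrent therapy for their tumor".

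Two cardiac warnings come close. Section 5.4.3.7 says "Avoid combination with other drugs with potential to lead to prolongation of QTc interval, if possible". Section 8.3.8 says HCQ/placebo "should not be administered with other drugs that have the potential to induce cardiac arrhythmias".

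**The concern.** Section 1.1 treats the chloroquine derivatives as one class with one lysosomal target (PPT1) and as the only clinically available drugs against autophagy. Section 1.2 promises a placebo control with no crossover on study. The co-medication rules do not protect that contrast. Table 17 considers chloroquine only as a drug whose own effect dabrafenib might weaken, not as a relative of the study drug.

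The protocol itself recognises non-cancer use: Section 8.3.9 mentions chronic HCQ treatment in lupus and juvenile arthritis, and Section 8.3.8 mentions other antimalarials.

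Two things are at stake:

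- **Control arm.** A placebo patient on non-study HCQ or chloroquine receives the class under test and still counts in the primary endpoint, because Section 5.8 follows every patient to progression. Any benefit in such a patient shrinks the observed difference.
- **HCQ arm.** Such a patient adds non-study drug to a starting dose of 1,200 mg/day (600 mg twice daily, Section 5.1.4), and the blind hides the duplication. Section 5.1.5 limits HCQ/placebo to 2 years, with a monitored exception, because of retinal toxicity. Section 8.3.10 lists irreversible retinopathy, QT prolongation and torsade de pointes.

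**Working it through.** **Do the rules permit it?** Take a patient on HCQ or chloroquine for a non-cancer illness.

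1. 3.1.6.3 does not apply, because the drug is not being given as an anticancer therapy.
2. 3.1.21 does not apply, because it is not therapy for the tumour.
3. 3.1.24 does not apply, because neither drug is in Table 16.
4. On study, chloroquine falls under Table 17 (monitor or substitute) and HCQ under the last sentence of 5.1.6.

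The patient can be enrolled and can continue the drug. Because treatment is blinded, this is the same in both arms.

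**How large could the dilution be?** Inputs from Section 9.3: one-year PFS 20% (control) and 45% (HCQ), 80 evaluable patients randomised 1:1 (40 per arm), one-sided alpha 0.10, Fisher's exact test for sizing. From Section 9.4: the planned test divides the difference in one-year rates by the square root of the summed variances. Early censoring is expected in fewer than 4 of 84 patients and is ignored here, so the Kaplan-Meier rates become simple proportions.

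The documents do not give the number of exposed controls (k) or the share of the planned benefit that each would gain (b). Both are assumptions:

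control rate = 0.20 + 0.25 × b × k/40

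true difference = 0.45 − control rate

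For example, k = 4 and b = 1 gives 0.20 + 0.25 × 4/40 = 0.225, a difference of 22.5 points.

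Power was found by summing the binomial probabilities of all outcomes in which each test rejects.

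*The plan's own figure first:* k = 0 with Fisher's test gives 81.69%, which matches the stated 81.7%. The planned unpooled test, enumerated in the same way, gives 87.8%. The large-sample formula for that test gives 88.4%; the gap is approximation error.

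| Exposed controls (of 40) | Benefit gained (b) | Control rate | Difference (points) | Fisher power | Planned test power |
|---|---|---|---|---|---|
| 0 | – | 20.0% | 25.0 | 81.7% | 87.8% |
| 1 | full | 20.6% | 24.4 | 79.8% | 86.3% |
| 2 | full | 21.25% | 23.8 | 77.8% | 84.7% |
| 4 | full | 22.5% | 22.5 | 73.7% | 81.3% |
| 1 | half | 20.3% | 24.7 | 80.8% | 87.1% |
| 2 | half | 20.6% | 24.4 | 79.8% | 86.3% |
| 4 | half | 21.25% | 23.8 | 77.8% | 84.7% |

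At full benefit, each exposed control costs about 2 points of Fisher power and 1.5 to 1.7 points with the planned test.

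**Type I error.** If the class has no effect, exposure changes neither arm's rate, so the false-positive rate is not raised.

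**The case against.** The strongest reply is that the gap is already partly closed. Section 8.3.8 says HCQ/placebo should not be combined with arrhythmogenic drugs, and the protocol puts HCQ in that group: it reports QT prolongation (8.3.8) and ventricular arrhythmias (8.3.10). An investigator could be expected to apply this to a second drug of the class. Section 5.4.3.7 adds monthly ECGs and a review of QT-prolonging co-medication when QTcB reaches 501 msec. Section 5.7 ends protocol therapy when non-protocol therapies are given. The closing sentence of 5.1.6 cannot be meant literally, since it would then readmit the drugs banned in Table 16.

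These texts lower the chance of exposure but do not amount to a ban:

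- 8.3.8 is a general warning outside the co-medication rules, and 3.1.24 does not screen against it. It cannot work as a strict prohibition, since 5.4.3.7 says that dabrafenib and trametinib themselves prolong QTc. Table 17 also names chloroquine as usable, so a site gets conflicting instructions.
- 5.4.3.7 is qualified by its own last two words.
- 5.7 leaves its term undefined, and it cannot readily cover medicines that 5.1.6 permits. It would stop study treatment, not the non-study drug.

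The reply on size is stronger, and much of it stands. Nothing in the documents suggests that such use is common. If it is a baseline trait, randomisation splits users between the arms, so 1, 2 or 4 exposed controls imply about 2, 4 or 8 users among 80 patients (2.5%, 5% or 10%). Full benefit is generous if doses for other illnesses are below 1,200 mg/day, and any induction that lowers chloroquine levels would reduce it further. Even the worst row leaves the planned test at 81.3%, close to the 81.7% design power. The bias runs against HCQ, in a phase II trial that Section 1.1 says is not for registration.

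**Conclusion.** The concern holds. Under the stated rules a patient taking HCQ or chloroquine for a non-cancer illness can be randomised to either arm and stay on the drug. The permission is explicit for chloroquine (with caution). For HCQ it follows from the general permission in 5.1.6 and the absence of any ban.

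The effect on the primary comparison is unknown and probably small. With up to 4 of 40 controls exposed, the losses shown are at most 8.0 points of Fisher power (81.7 − 73.7) and 6.5 points with the planned test (87.8 − 81.3). These figures assume the planned 20% and 45% rates, no censoring and full benefit in every exposed control. At half benefit they are 3.9 points (81.7 − 77.8) and 3.1 points (87.8 − 84.7). The point about double exposure in the HCQ arm does not depend on those assumptions about benefit.

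This is worth correcting because the remedy is cheap, not because the primary result is likely to turn on it.

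**What to change.** Add non-study hydroxychloroquine and chloroquine to the prohibited list in Section 5.5, and delete chloroquine from Table 17. Criterion 3.1.24 then excludes current users without further wording, and the on-study rules cover later use. How to manage an individual patient who comes to need such a drug stays with the investigator. It would also help to record any such use by arm, so that the final report can show whether the control arm was affected.

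The cost is a few lines in an amendment. The downside is that the occasional patient already on HCQ for another illness would not be enrolled.
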